2.11 PD and PK/PD analyses

The secondary PD objective is to assess immunogenicity of LAG525 and spartalizumab in the three investigated combinations.

[REDACTED]

2.11.1 Immunogenicity

2.11.1.1 Sample ADA Status

Each IG sample is assessed in a three tiered anti-drug anti-body (ADA) testing approach. All IG samples are analyzed in the initial screening assay (first tier). Samples testing negative in the screening assay are not subject to a confirmatory assay. Samples testing positive in the screening assay are then subjected to the confirmatory assay to demonstrate that ADA are

specific for the therapeutic protein product (second tier). The titer of confirmatory positive samples will be subsequently determined in the titration assay (third tier). Samples identified as positive in the confirmatory assay are considered ADA positive and are further characterized in the neutralization assay to indicate the presence of neutralizing antibodies (NAb). Samples can test negative in either the screening or confirmatory assay but for analysis purposes they are not differentiated. The following properties of each sample will be provided in the source data:

- Result of assay according to pre-specified confirmatory cut point: ADA positive (yes) or ADA negative (no)
- Titer (for positive samples): numerical representation of the magnitude of ADA response
- Drug tolerance level: highest drug concentration that does not interfere in the ADA detection method
- Fold titer change (i.e. x-fold): threshold for determining treatment boosted

Determinant samples are defined as samples which are not unevaluable (where unevaluable = sample where assay is not available).

The following definitions apply only to determinant samples:

- *ADA-negative sample*: Determinant sample where assay is ADA negative and respective drug (i.e. LAG525 or spartalizumab) PK concentration at the time of IG sample collection is less than the drug tolerance level.
- *ADA-positive sample*: Determinant sample where assay is ADA positive.
- *ADA-inconclusive sample*: Sample where assay is ADA negative and LAG525 (PDR001) PK concentration at the time of IG sample collection is greater than or equal to the drug tolerance level or missing.

The following definitions apply only to post-baseline ADA-positive samples with a corresponding determinant baseline sample. To be classified as *treatment-boasted* or *treatment-unaaffected*, both the post-baseline and baseline titer must be non-missing:

- *treatment-induced ADA-positive sample*: ADA-positive sample post-baseline with ADA-negative sample at baseline.
- *treatment-boasted ADA-positive sample*: ADA-positive sample post-baseline with titer that is at least *the fold titer change* greater than the ADA-positive baseline titer.
- *treatment-unaaffected ADA-positive sample*: ADA-positive sample post-baseline with titer that is less than *the fold titer change* greater than the ADA-positive baseline titer.

NOTE: PK concentrations which are flagged for exclusion will still be used to determine ADA-inconclusive and ADA-negative samples.

The following summaries of ADA sample status (n and %) will be provided using *Immunogenicity prevalence set*:

- ADA-positive samples (i.e. ADA prevalence) and ADA-positive NAb samples, both overall and by time point (including baseline). For summaries by time point, the denominator is the number of subjects at that time point with a determinant sample.

Listings will be provided of sample ADA status (including titer for positive samples).

2.11.1.2 Subject ADA status

Subject ADA status will be defined for both investigational drugs LAG525 and spartalizumab, based on their respective sample ADA status and respective PK concentrations. Any IG sample collected after 150 days of the last dose of the respective drug (i.e. LAG525 or spartalizumab) will not be used for summaries or derivations and will only be included in the listing.

[figure not shown]
Subject ADA status is defined as follows:

- *Treatment-induced ADA-positive subject*: subject with ADA-negative sample at baseline and at least one treatment-induced ADA-positive sample.
- *Treatment-boosted ADA-positive subject*: subject with ADA-positive sample at baseline and at least one treatment-boosted ADA-positive sample.
- *Treatment-unaffected ADA-positive subject*: subject with ADA-positive sample at baseline, no treatment-boosted ADA-positive samples, and at least one treatment-unaffected ADA-positive sample.
- *Treatment-reduced ADA-positive subject*: subject with ADA-positive sample at baseline and at least one post baseline determinant sample, all of which are ADA-negative samples.
- *ADA-negative subject*: subject with ADA-negative sample at baseline and at least one post baseline determinant sample, all of which are ADA-negative samples.
- *Inconclusive subject*: subject who does not qualify as treatment-induced ADA-positive, treatment-boosted ADA-positive, treatment-unaffected ADA-positive, treatment-reduced ADA-positive, or ADA-negative.

The following summaries of ADA subject status (n and %) will be provided using *Immunogenicity incidence set*:

[figure not shown]
- Treatment-boosted ADA-positive subjects; denominator is the number of subjects with ADA-positive sample at baseline.
- Treatment-induced ADA-positive subjects; denominator is the number of subjects with ADA-negative or ADA- inconclusive sample at baseline.
- ADA-inconclusive subjects: denominator is the number of subjects in Immunogenicity incidence set.
- ADA-negative subjects: denominator is the number of subjects in *Immunogenicity incidence set*.
- ADA-positive subjects (i.e. ADA incidence): calculated as the number of treatment-boosted ADA-positive and treatment-induced ADA-positive subjects; denominator is the number of subjects in *Immunogenicity incidence set*.

[figure not shown]
Listings will be provided of subject ADA status.

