5.2 Exclusion criteria

Participants meeting any of the following criteria are not eligible for inclusion in this study.

- 1. Patient has received prior immune checkpoint inhibitors as anticancer treatment, such as anti-LAG-3, anti-PD-1, anti-PD-L1, or anti-PD-L2 antibody (any line of therapy).
- 2. Patient received prior neoadjuvant or adjuvant therapy with a platinum agent or mitomycin and experienced recurrence within 12 months after the end of the platinum-based or mitomycin containing therapy, or received platinum or mitomycin for advanced disease.
- 3. Patient is concurrently using other anti-cancer therapy.
- 4. Patient has had major surgery within 14 days prior to starting study treatment or has not recovered to grade 1 or less from major side effects.
- 5. Patient with presence of CTCAE grade 2 toxicity or higher due to prior cancer therapy. Exception: Patients with any grade of alopecia are allowed to enter the study.
- 6. Patient has received radiotherapy ≤ 4 weeks prior to randomization (≤ 2 weeks for limited field radiation for palliation), and has not recovered to grade 1 or better from related side effects of such therapy (with the exception of alopecia).
- 7. Patient has a known hypersensitivity to other monoclonal antibodies, platinum-containing compounds, or to any of the excipients of LAG525, spartalizumab, or carboplatin.
- 8. Patient with history of Stevens-Johnson Syndrome or Toxic Epidermal Necrolysis, or a history of severe hypersensitivity reactions, which in the opinion of the investigator may pose an increased risk of serious infusion reaction.
- 9. History of acute pancreatitis within 1 year of screening or past medical history of chronic pancreatitis.
- 10. Clinically significant cardiac disease or impaired cardiac function, including any of the following: Cardiac or cardiac repolarization abnormality, including any of the following:
 - i. History of myocardial infarction (MI), angina pectoris, coronary artery bypass graft (CABG) within 6 months prior to randomization
 - ii. History or current diagnosis of myocarditis
 - iii. Cardiac troponin T (TnT) or I (TnI) elevated > 2 x ULN at screening. Repeat Troponin test if values are between >1 and 2 x ULN
 - Patients with a screening or repeat levels $\leq 1 \times \text{ULN}$ may be included.
 - If repeat Troponin levels are > 1 and < 2 x ULN, patient can be included at the investigator's discretion after cardiac assessment

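### A missing PK value at the pre-dose baseline makes an ADA-negative sample inconclusive, so a participant who later seroconverts counts in the ADA denominators but in neither numerator

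*SAP*

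**What the plan says.** Immunogenicity is a secondary objective, with ADA prevalence at baseline and ADA incidence on treatment as endpoints (Protocol Table 2-1; SAP Table 1-1). Protocol 12.5.4 leaves the details to the SAP, so the SAP rules define the result.

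- **Sample status (SAP 2.11.1.1).** An assay-negative sample is ADA-negative only if the "PK concentration at the time of IG sample collection is less than the drug tolerance level". It is ADA-inconclusive if the "PK concentration at the time of IG sample collection is greater than or equal to the drug tolerance level or missing". A positive assay needs no PK check. A sample is determinant as long as an assay result exists, so an inconclusive sample is still determinant.
- **Treatment-induced numerator.** The sample-level definition is "ADA-positive sample post-baseline with ADA-negative sample at baseline"; the subject-level definition is "subject with ADA-negative sample at baseline and at least one treatment-induced ADA-positive sample".
- **Treatment-induced denominator (SAP 2.11.1.2).** The "denominator is the number of subjects with ADA-negative or ADA- inconclusive sample at baseline".
- **Overall ADA incidence (SAP 2.11.1.2).** Treatment-boosted plus treatment-induced participants, divided by the whole incidence set. SAP 2.2 defines that set by a determinant baseline sample and at least one determinant post-baseline sample.
- **Residual class.** Anyone who fits no other subject category is inconclusive.
- **PK handling (SAP 2.10).** Values below the quantification limit are set to zero; missing values are not imputed.
- **Baseline sample.** Protocol Table 8-7 schedules it before infusion on Cycle 1 Day 1. The first exclusion criterion in Protocol 5.2 is "Patient has received prior immune checkpoint inhibitors as anticancer treatment, such as anti-LAG-3"; it goes on to name anti-PD-1, in any line of therapy.

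**The concern.** The PK condition exists because circulating drug can mask antibodies, so a negative assay at high drug concentration proves little. That reason is absent before the first dose in a participant who has never had an antibody of either class. A missing pre-dose PK value then says nothing about whether the negative assay can be trusted, yet it changes the participant's class.

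The treatment-induced rate also mixes two definitions: baseline-inconclusive participants are included below the line and barred above it. The adjacent treatment-boosted rate has no such mismatch, since both its parts require a positive baseline. At stake is a descriptive secondary result. A real seroconversion can be left out of the incidence count and shown as inconclusive.

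**Working it through.** The plan states no ADA rate, count or precision target, so there is no figure to reproduce. The check is a trace of the rules, followed by the algebra of the two rates.

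**Step 1: two participants who differ only in baseline PK.** Both are assay-negative before infusion on Cycle 1 Day 1, and both have an ADA-positive sample later.

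| | Participant A | Participant B |
|---|---|---|
| Baseline PK | measured, below quantification limit, set to zero | missing, not imputed |
| Baseline sample status | ADA-negative | ADA-inconclusive |
| In incidence set | yes | yes (assay result exists) |
| In treatment-induced denominator | yes | yes |
| Treatment-induced | yes | no (baseline is not ADA-negative) |
| Boosted, unaffected or reduced | no | no (each needs a positive baseline) |
| Subject status | treatment-induced | inconclusive |
| In overall incidence numerator | yes | no |

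**Step 2: all combinations.** Take an assay-negative baseline with PK either at or above tolerance or missing (2 routes). Cross this with four post-baseline patterns: positive only, negative only, inconclusive only, negative then positive. All 2 × 4 = 8 cases are in the treatment-induced denominator, all are classed inconclusive, and none reaches a numerator. Changing only baseline PK from below tolerance to missing moves both patterns containing a positive from treatment-induced to inconclusive. It also moves the negative-only pattern from ADA-negative to inconclusive.

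**Step 3: size.** Let Nneg and Ninc be the baseline ADA-negative and baseline-inconclusive counts (all Ninc through missing pre-dose PK), X the treatment-induced count under the SAP, and S the number among the Ninc with an ADA-positive post-baseline sample.

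- Planned rate = X / (Nneg + Ninc).
- Rate when the pre-dose negatives are classed ADA-negative = (X + S) / (Nneg + Ninc).
- Shortfall = S / (Nneg + Ninc). For overall ADA incidence it is S divided by the size of the incidence set.

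X, S, Nneg and Ninc are not in the documents. The Amendment 4 summary gives 20, 34 and 34 randomised by arm, and the denominators cannot exceed these. Each missed seroconversion (S = 1) therefore lowers the arm's rate by at least 1/20 = 5.0 percentage points in Arm 1 and 1/34 = 2.9 points in Arms 2 and 3. With S = 0 both rates are unchanged.

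If missing PK is unrelated to seroconversion, the planned treatment-induced rate is on average Nneg / (Nneg + Ninc) times the rate after reclassification. With an assumed denominator of 34 and assumed Ninc of 0, 2, 3 and 7, the factor is 34/34 = 1.00, 32/34 = 0.94, 31/34 = 0.91 and 27/34 = 0.79. These counts only show the scale; nothing in the documents says which applies.

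**The case against.** The strongest reply is that this will seldom happen and that little is hidden. Protocol Table 8-7 has PK and immunogenicity blood drawn together. A measured drug-free sample becomes zero and so ADA-negative, and PK values flagged for exclusion are still used for ADA status. Only a truly missing PK value beside an available assay result triggers the rule. Positive samples still appear in the prevalence summaries and the listings with titers, and the number of inconclusive participants is tabulated. No decision rule uses ADA.

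Most of that stands, and it limits the size. It does not repair the classification. The planned table does not separate participants inconclusive at baseline from those inconclusive later, so a reader could find a missed seroconverter only by going through the listings.

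Three stronger readings are tempting and not supported.

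- **That all ADA rates are diluted.** Prevalence is a sample-level summary, and the treatment-boosted rate requires a positive baseline; this rule touches neither.
- **That removing these participants from the denominator shows the true rate.** Once a pre-dose negative is classed ADA-negative, the participant returns to the denominator. The rate rises only if one of them seroconverted.
- **That overall incidence should be restricted to conclusive participants.** For someone negative at baseline, one positive sample is enough to be conclusive, whereas ADA-negative status needs every post-baseline sample to be negative. Those inconclusive only after baseline thus have no positive sample, and removing them can only raise the rate. Dividing by the full incidence set is defensible, and the other figure can be computed from the planned table.

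**Conclusion.** The point holds as a narrow classification error with a matching numerator and denominator fault. On the SAP's wording, a missing PK value alone turns a pre-dose assay-negative baseline into an inconclusive one. That bars the participant from the treatment-induced and overall incidence numerators while keeping them in both denominators. The two rates can be understated and cannot be overstated by this route. The effect is zero if no such participant exists or none seroconverts; otherwise it is at least 2.9 points per missed seroconversion in Arms 2 and 3, and 5.0 in Arm 1.

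This rests on the baseline sample having been drawn before the first dose and on the exclusion of prior anti-LAG-3 and anti-PD-1 treatment having been respected. The number affected is unknown and probably small. The consequence is confined to a descriptive secondary endpoint; the primary response analysis is untouched.

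**What to change.** Make two changes to the SAP.

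1. In 2.11.1.1, state that an assay-negative baseline sample confirmed as taken before the first dose of the respective antibody is ADA-negative even when its PK value is missing. Keep the inconclusive rule for post-baseline samples.
2. In 2.11.1.2, limit the treatment-induced denominator to participants with an ADA-negative baseline sample, so that it matches the numerator. After the first change, this removes only participants who remain inconclusive at baseline for another reason.

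The cost is a few lines of SAP text and a small derivation change, with no new data. The downside is reliance on the sample being truly pre-dose. Protocol 8.5.1.1 requires exact dates and clock times for dosing and for PK and immunogenicity draws, so this can be checked for each participant. Where the times do not confirm it, the sample should stay inconclusive. Any ADA table already produced under the present rule should be rerun or footnoted if an affected participant is found.

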2.12 Patient-reported outcomes

Not applicable.

2.15 Interim analysis

No formal interim analysis is planned for this trial. The primary analysis of the study data will be reported in the primary CSR based on all subjects' data up to the time when all subjects have been followed for efficacy (tumor assessments) for at least 24 weeks or discontinued tumor assessments for any reason prior to 24 weeks. Any additional data (e.g., DoR, OS, safety) for subjects continuing to receive study treatment past the data cut-off date for the primary CSR, as allowed by the protocol, will be reported in the final analysis on completion of the study.

3 Sample size calculation

3.1 Primary analysis

The sample size calculation is based on the primary variable ORR considering the statistical model, hypothesis and method of analysis detailed in [Section 2.5](#). Proof of preliminary efficacy (PPE) for each drug combination (study arm) will be declared if both of the following conditions are met:

- the mean of the posterior distribution of ORR is at least 35%
- and
- the posterior probability that the ORR is $\geq 25\%$ is at least 0.9

Approximately 32 subjects will be enrolled in each arm for a total of approximately 96 subjects. In a given arm of 32 subjects, the type-I error rate is 8% while the probability of declaring proof of preliminary efficacy (PPE) is at least 80% for ORR $\geq 45\%$ ([Table 3-1](#)).

Table 3-1 Operating characteristics with 32 subjects in each arm

True ORR	Probability of declaring PPE in each arm (12 or more responders)	Probability of missing PPE (11 or less responders) in each arm
25 %	0.079	0.921
30 %	0.228	0.772
35 %	0.448	0.552
40%	0.675	0.325
45 %	0.847	0.153

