Study design	This is a phase 2, randomized, open-label, 3-arm, multicenter global study. With protocol amendment 3, enrollment to treatment Arm 1 (LAG525 + spartalizumab) was prematurely closed and subsequent enrolled participants will be randomized to Arms 2 and 3 only.
Study population	The study will include approximately 84 adult participants (after amendment 3) with advanced (loco-regionally recurrent not amenable to curative therapy or metastatic) TNBC which progressed after adjuvant or one prior line of systemic therapy for metastatic disease and never received prior treatment with an immune checkpoint inhibitor.

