6.3.2 Treatment assignment, randomization

Participants were assigned to one of the three treatment arms in a ratio of 1:1:1. Starting with protocol amendment 3, participants will be assigned to Arm 2 and Arm 3 only in a ratio of 1:1 (Section 3 and Section 6.1).

Randomization will be stratified by the presence of liver metastasis and line of therapy (first line or second line).

The randomization numbers will be generated using the following procedure to ensure that treatment assignment is unbiased. A participant randomization list will be produced by the Interactive Response Technology (IRT) provider using a validated system that automates the random assignment of participant numbers to randomization numbers. Random permuted blocks scheme will be used for this study. The randomization numbers are linked to the different treatment arms, which in turn are linked to medication numbers. A separate medication randomization list will be produced by or under the responsibility of Novartis Drug Supply Management using a validated system that automates the random assignment of medication numbers to medication packs containing each of the study treatments.

Prior to dosing, all participants who fulfill all inclusion/exclusion criteria will be randomized via IRT to one of the treatment arms. The investigator or his/her delegate will call or log on to the IRT and confirm that the participant fulfills all the inclusion/exclusion criteria. The IRT will assign a randomization number to the participant, which will be used to link the participant to a treatment arm and will specify a unique medication number for the first package of study treatment to be dispensed to the participant. The randomization number will not be communicated to the caller.

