12.8 Sample size calculation

12.8.1 Primary endpoint(s)

The sample size calculation is based on the primary variable ORR considering the statistical model, hypothesis and method of analysis detailed in Section 12.4.2. Proof of preliminary efficacy (PPE) for each drug combination (study arm) will be declared if both of the following conditions are met:

- the mean of the posterior distribution of ORR is at least 35% and
- the posterior probability that the ORR is $\geq 25\%$ is at least 0.9

Approximately 32 participants were planned to be enrolled in each arm for a total of approximately 96 participants. In a given arm of 32 participants, the type-I error rate is 8% while the probability of declaring proof of preliminary efficacy (PPE) is at least 80% for ORR ≥ 45% (Table 12-2). With protocol amendment 3, enrollment to treatment Arm 1 (LAG525 + spartalizumab) was prematurely closed. Therefore, approximately 84 participants will be enrolled (approximately 20 participants in Arm 1, and 32 participants per arm for Arms 2 and 3).

Table 12-2 Operating characteristics with 32 participants in each arm

True ORR	Probability of declaring PPE in each arm (12 or more responders)	Probability of missing PPE (11 or less responders) in each arm
25 %	0.079	0.921
30 %	0.228	0.772
35 %	0.448	0.552
40%	0.675	0.325
45 %	0.847	0.153

13 Ethical considerations and administrative procedures

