mL	milliliter
NCI	National Cancer Institute
NMQ	Novartis MedDRA Queries
o.d.	Once Daily
ORR	Overall Response Rate / Objective Response Rate
OS	Overall Survival
PAS	Pharmacokinetic Analysis Set
PD	Progressive Disease
PD-1	Programmed Death 1
PD-L1	Programmed Death-Ligand 1
PD-L2	Programmed Death-Ligand 2
PDI	Planned Dose Intensity
PFS	Progression-Free Survival
PgR	Progesterone receptor
PK	Pharmacokinetics
PR	Partial Response
PRO	Patient-reported Outcomes
PT	Preferred Term
qd	Qua'que di'e / once a day
RDI	Relative Dose Intensity
RAP	Report and Analysis Process
RECIST	Response Evaluation Criteria in Solid Tumors
sd	Standard deviation
SD	Stable Disease
SAE	Serious Adverse Event
SAP	Statistical Analysis Plan
SMQ	Standardized MedDRA Queries
SOC	System Organ Class
SOD	Sum Of Diamaters
TA	Tumor Assessment
TBL	Total Bilirubin
TFLs	Tables, Figures, Listings
████	████████████████████
TNBC	Triple Negative Breast Cancer
TP	Time Point
TTR	Time To Response
ULN	Upper Limit of Normal
UNK	Unknown

WHO	World Health Organization
WHO-DD	WHO-Drug Dictionary
WHO DRL	WHO Drug Reference Listing

1 Introduction

This statistical analysis plan (SAP) describes all planned analyses for the clinical study reports (CSR, either CSR for the primary analysis or CSR for the final analysis) of study CLAG525B2101, a phase II, randomized, open-label, three-arm multicenter study of LAG525 given in combination with spartalizumab (PDR001), or with spartalizumab and carboplatin, or with carboplatin, as first or second line therapy in patients with advanced triple-negative breast cancer.

The content of this SAP is based on protocol CLAG525B2101 v04. All decisions regarding final analysis, as defined in the SAP document, have been made prior to database lock of the study data. This SAP has been amended before the final close-out CSR for safety and PK analysis, for which no inferential analysis is planned.

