1.1 Study design

This is a randomized, phase II, open-label, three-arm, multicenter study evaluating the safety and efficacy of LAG525 given in combination with spartalizumab, or LAG525 with spartalizumab and carboplatin, or LAG525 with carboplatin, as first or second line therapy in patients with advanced triple-negative breast cancer. Approximately 96 subjects will be randomized to one of the following treatment arms in 1:1:1 ratio:

- LAG525 + PDR001
- LAG525 + PDR001 + carboplatin
- LAG525 + carboplatin

Randomization will be stratified by the following factors:

- Presence of liver metastasis (Yes / No)
- Line of therapy (First line: following disease progression after adjuvant or neoadjuvant therapy / Second line: following one disease progression in advanced or metastatic setting)

[figure not shown]
With protocol amendment 3, enrollment to treatment Arm 1 (LAG525 + PDR001) was prematurely closed. Novartis and the study steering committee decided to prematurely stop enrollment of subjects to Arm 1 after data review showed an increased treatment discontinuation rate due to progressive disease in Arm 1 as compared to Arms 2 and 3 (both containing carboplatin)

Overall response rate (ORR), as assessed by local investigators review of tumor response and using RECIST 1.1 criteria, is the primary endpoint in this study.

The primary analysis was conducted when all subjects have been followed for efficacy (tumor assessments) for at least 24 weeks or discontinued tumor assessments for any reason prior to 24 weeks. The primary analysis data will be summarized in the primary clinical study report (CSR). Any additional data for subjects continuing to receive study treatment past the data cut-off date for the primary CSR, as allowed by the protocol, will be reported in the final CSR on completion of the study.

No formal interim analysis is planned for this trial.

Figure 1-1 Study Design

[figure not shown]
**With protocol amendment 3, enrollment to treatment Arm 1 (LAG525 + spartalizumab) was prematurely closed
 Δ Upon the release of protocol amendment #4, ongoing patients who will transfer into PTA program (roll over study or PSDS) only EOT visit will be performed but no safety, efficacy and survival follow-up
 + Patients who had stopped study treatment more than 150 days will be discontinued from the study – see Section 9.1.1 for details. Survival follow-up period is removed after protocol amendment #4 is approved

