3.2 Power for analysis of key secondary variables

Not applicable.

4 Change to protocol specified analyses

Not applicable.

5 Appendix

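### SAP sections 1.1 and 3.1 still describe the superseded design (96 subjects, 32 per arm, 1:1:1), and the operating characteristics given for 32 do not both hold in any arm analysed

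*SAP*

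**What the plan says.** The SAP introduction ties the document to the current protocol: "The content of this SAP is based on protocol CLAG525B2101 v04". Its design and sample size text is nevertheless the plan from before amendment 3:

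- SAP 1.1: "Approximately 96 subjects will be randomized to one of the following treatment arms in 1:1:1 ratio". A later paragraph of the same section reports the early closure of Arm 1 but leaves the total and the ratio as they were.
- SAP 3.1: "Approximately 32 subjects will be enrolled in each arm for a total of approximately 96 subjects". It continues "In a given arm of 32 subjects, the type-I error rate is 8" percent, with at least 80% probability of declaring proof of preliminary efficacy (PPE) when the true response rate (ORR) is 45% or more. Table 3-1 gives the detail for 32 subjects. Section 3.1 does not mention the closure.
- SAP section 4, headed "Change to protocol specified analyses", is marked as not applicable.

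Protocol version 04 differs. Section 12.8.1 puts the 96-participant plan in the past tense and replaces it with about 84, made up of "approximately 20 participants in Arm 1, and 32 participants per arm for Arms 2 and 3"; the protocol summary gives the same total. On allocation, section 6.3.2 says that from amendment 3 "participants will be assigned to Arm 2 and Arm 3 only in a ratio of 1:1". The status statement for amendment 4 reports 20, 34 and 34 randomized to Arms 1, 2 and 3.

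SAP 5.4.1 says the criteria are judged on the number actually enrolled, and uses 32 only as an example.

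**The concern.** A SAP that names version 04 as its basis should not give a sample size and allocation ratio that version 04 has withdrawn. This is current SAP text, not an amendment history, and section 1.1 is at odds with itself once it reports the closure.

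The mismatch also reaches the operating characteristics. They are given for 32 only, while the rule is applied at 20, 34 and 34. The responder cut moves in whole steps, so a change of two subjects can shift the error rate noticeably. Someone reading the negative result against the SAP would attach roughly 8% error and 85% power at ORR 45% to arms that have neither figure.

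**Working it through.** **Inputs.** Prior Beta(0.35/0.65, 1) = Beta(0.5385, 1), from protocol Appendix 2 and SAP 5.4.1. PPE requires a posterior mean of at least 0.35 and Pr(ORR ≥ 25% | data) of at least 0.90 (SAP 3.1). The null ORR is 25%. Arm sizes are 32 (design) and 20/34/34 (randomized). The full analysis set (FAS) is defined by randomization, so it is taken as everyone randomized.

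**Totals.** 3 × 32 = 96 (SAP). 20 + 32 + 32 = 84 (protocol plan). 20 + 34 + 34 = 88 (randomized).

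**Method.** For y responders out of n, the posterior is Beta(0.5385 + y, 1 + n − y), with mean (0.5385 + y)/(1.5385 + n). The cut r is the smallest y that meets both criteria. The probability of PPE is then the exact binomial tail Pr(X ≥ r) at each true ORR.

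**Cuts.**

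- n = 32, y = 12: mean 12.5385/33.5385 = 0.3739, probability 0.9385 (SAP 5.4.1 gives 0.939). y = 11 fails: mean 0.3440, probability 0.8783. Cut 12, as in Table 3-1.
- n = 34, y = 12: mean 12.5385/35.5385 = 0.3528, probability 0.9063. y = 11 fails: mean 0.3247, probability 0.8288. The cut stays at 12.
- n = 20, y = 8: mean 8.5385/21.5385 = 0.3964, probability 0.9256. y = 7 has a mean of exactly 0.3500 but a probability of only 0.8352, so it fails the second criterion. Cut 8.

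**Probability of declaring PPE.**

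| True ORR | SAP Table 3-1 (n = 32, simulated) | n = 32, exact | n = 34, cut 12 | n = 20, cut 8 (nominal) |
|---|---|---|---|---|
| 25% | 0.079 | 0.0804 | 0.1193 | 0.1018 |
| 30% | 0.228 | 0.2283 | 0.3068 | 0.2277 |
| 35% | 0.448 | 0.4485 | 0.5500 | 0.3990 |
| 40% | 0.675 | 0.6767 | 0.7669 | 0.5841 |
| 45% | 0.847 | 0.8487 | 0.9060 | 0.7480 |

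The plan's own figures reproduce. Table 3-1 comes from 100,000 simulated trials and agrees with the exact values to within simulation error. At n = 34 the error exceeds 8% and power is better than stated. At n = 20 the error exceeds 8% and power falls below 80%.

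**Does protocol Table 16-1 fill the gap?** It covers 32, 36 and 40. Taking the midpoint of the rows for 32 and 36 as a guess for 34 gives (0.079 + 0.092)/2 = 0.0855 for error and (0.847 + 0.893)/2 = 0.870 for power. The exact error of 0.119 is above every error in that table (0.079, 0.092, 0.102), because the cut is still 12 at 34 but has risen to 13 by 36.

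**Sensitivity to the FAS.** SAP Table 2-2 allows exclusion for lack of written consent. One exclusion per arm would give n = 33, cut 12: 9.9% error and 88.0% power; and n = 19, cut 8: 7.8% and 68.3%. In each case one of the two stated properties still fails.

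**The case against.** The case for leaving this alone is reasonable. SAP 3.1 says explicitly that its figures are for an arm of 32, Table 3-1 carries the same label, and enrolment is described as approximate; nothing there assigns 8% to an arm of 34 or 20. Section 5.4.1 already applies the rule at the actual size, section 1.1 discloses the Arm 1 closure, and arm sizes will appear in planned outputs. The introduction says the SAP was amended for a close-out report on safety and PK with no inferential analysis, so nothing still to be run depends on section 3.1. Protocol 12.8.1 also tabulates only 32, so the missing rows are not a disagreement between the two documents. With a negative result the miss probability matters more than false positives, and at n = 34 and ORR 45% it is 9.4% against the 15.3% tabulated, so the SAP errs on the cautious side for the two completed arms. Finally, a row for n = 20 does not describe Arm 1's true behaviour.

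Most of this stands as a limit on the consequences. Table 3-1 and the decision rule are sound, and the section 4 entry is weak evidence, since that section concerns analyses rather than enrolment. None of it makes the total, the per-arm size or the ratio correct. An approximate 32 may cover a headcount of 34, but it does not cover 20 in Arm 1, a total of 96, or 1:1:1 allocation. A SAP revised after the randomized numbers were known should not state them as the current plan.

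**Conclusion.** The concern holds. SAP 1.1 and 3.1 misstate the planned size and allocation of the design they claim to follow: 96 against 84 planned, with 88 randomized. The 8% error and at-least-80% power, both right for 32, do not hold together in any arm. In Arms 2 and 3 the error is 11.9%, about half as large again as stated, with power of 90.6% at ORR 45%. In Arm 1 the nominal figures are 10.2% and 74.8%.

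The practical effect is on interpretation only. The protocol reports that no arm met PPE, and these figures do not change that. At ORR 35%, the minimum rate of interest, the shift for n = 20 is small (0.399 against 0.448).

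Two assumptions matter: the FAS equals all randomized, and n is treated as fixed. The second does not strictly hold for Arm 1, which closed after a data review, so its figures are neither its actual error rate nor its actual miss probability.

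**What to change.** Change the SAP only.

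1. In sections 1.1 and 3.1, replace the total of 96, the 32 in every arm and the 1:1:1 ratio with the content of protocol 12.8.1 and 6.3.2: about 84 (20/32/32), allocated 1:1 to Arms 2 and 3 after amendment 3. State the randomized numbers, 20/34/34.
2. Keep Table 3-1 unchanged as the design-stage record.
3. Below it, or in the CSR, add the n = 34 (cut 12) and n = 20 (cut 8) columns from the working above as two rows rounded to three decimals, labelled as computed for realised sizes. Note on the n = 20 row that it is nominal: it treats n as fixed and ignores the data-driven closure of Arm 1. If the final FAS differs from the randomized numbers, recompute at the final n.

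The cost is wording in two SAP sections and two table rows. It needs no protocol amendment, no further patients, and no change to the decision rule.
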